7.11 Stopping rules

The study will be stopped if a) one death attributed to the procedure or the device, b) >2 of Grade IV AEs has occurred, and c) > 4 Grade III or more AEs occur.

Adverse Events

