25. Subjects with severe cardiopulmonary disease or other serious organic disease which might include known history of coronary artery disease, myocardial infarction within the past 6 months, poorly controlled hypertension, required use of NSAIDs.
26. Subjects taking medications on specified hourly intervals that may be affected by changes to gastric emptying, such as anti-seizure or anti-arrhythmic medications.
27. Subjects who are taking corticosteroids, immunosuppressants, and narcotics.
28. Symptomatic congestive heart failure, cardiac arrhythmia, or unstable coronary artery disease.
29. Pre-existing respiratory disease such as moderate or severe chronic obstructive pulmonary disease (COPD) requiring steroids, pneumonia, or cancer.
30. Diagnosis of autoimmune connective tissue disorder (e.g. Systemic lupus erythematosus, scleroderma) or immunocompromised.
31. Specific diagnosed genetic disorder such as Prader Willi syndrome.
32. Eating disorders including night eating syndrome (NES), bulimia, binge eating disorder, or compulsive overeating.
33. Known history of endocrine disorders affecting weight such as uncontrolled hypothyroidism.
34. At the discretion of the PI for subject safety
35. If minority inclusion population target of 10% has not been reached by the 90% enrollment mark (example 21 of 24 subjects), the remaining enrollments will be reserved for minority subjects (example 3 of 24 subjects).

TRIAL PROCEDURES

Informed Consent

Prior to being enrolled in the trial, study participants must consent to participate after the nature, scope, and possible risks of the trial have been explained and outlined in an understandable form to them per the requirements of the IRB. Participants are free to withdraw consent at any time.

After reading the Informed Consent Form (ICF) document, the participant must sign and date the latest approved version of the ICF before any study procedures are performed (electronic via compliant system such as DocuSign, or wet-signed copy prepared in Participant Tracking System (Ptrax). A copy of the signed consent document will be accessible for the participant, and the original signed consent form will be retained by the study team.

Where possible, “remote” visits such as via phone or video call will be acceptable across the schedule of events to streamline coordination efforts and adapt to any unexpected conditions such as isolation protocol.

Study Timeline

The study timeline is depicted in Figure 1.

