This study will adhere to an IRB approved data safety monitoring plan (DSMP) to ensure sufficient oversight of the following areas of study conduct: subject safety, data integrity, subject privacy, data confidentiality, product accountability, study documentation and study coordination. Monthly meetings will be held with the Principal Investigator in attendance to review study conduct, with additional meetings to occur as needed to address time sensitive matters including adverse events or any deviations. Internal monitoring will be conducted following the accrual of the first subject, with additional monitoring to be undertaken on a quarterly basis thereafter. All adverse events, deviations and unanticipated problems affecting subject safety will be reported according to the requirements of the IRB of record. Ongoing assessment of AEs by the PI will determine if any of the stopping rules have been triggered.

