7.2.1 Definitions

The following definitions will be used:

7.2.1.1 Adverse Events:

Only untoward medical occurrence, unintended disease or injury, or untoward clinical signs (including abnormal laboratory findings) related to the study intervention. Each subject will be followed closely to ensure safety.

Adverse events will be classified using the Clavien-Dindo classification in Figure 2.

Figure 2. Adverse Event (AE) Clavien-Dindo Classification Grading

Grade	Definition
Grade I	Any deviation from the normal postoperative course without the need for pharmacological treatment or surgical, endoscopic, and radiological interventions Allowed therapeutic regimens are: drugs as antiemetics, antipyretics, analgetics, diuretics, electrolytes, and physiotherapy. This grade also includes wound infections opened at the bedside
Grade II	Requiring pharmacological treatment with drugs other than such allowed for grade I complications Blood transfusions and total parenteral nutrition are also included
Grade III	Requiring surgical, endoscopic, or radiological intervention
Grade IIIa	Intervention not under general anesthesia
Grade IIIb	Intervention under general anesthesia
Grade IV	Life-threatening complication (including CNS complications) requiring IC/ICU management
Grade IVa	Single organ dysfunction (including dialysis)
Grade IVb	Multiorgan dysfunction
Grade V	Death of a patient

7.2.1.2. Serious Adverse Event (SAE):

An adverse event that meets one of the following criteria

- Led to death
- Resulted in serious deterioration in the health of the subject that results in:
 - Life-threatening illness or injury
 - Permanent impairment of a body structure or a body function
 - The need for in-patient care or prolongation of hospitalization (this does not include the optional 23 hours observation admission after ESG or re-tightening procedure).
 - Medical or surgical intervention to prevent life-threatening illness or injury or permanent impairment to a body structure or a body function.
- **Planned hospitalization for a pre-existing condition, or a procedure required by the trial protocol, without serious deterioration in health, is not considered a serious adverse event**

Unanticipated problems, SAEs and AEs will be reported to governing IRBs per local guidelines.

For the purpose of the study, an adverse event is considered severe if it is grade ≥ 3 on the Clavien-Dindo classification.

7.2.1.3 Device-Related Adverse Event (DRAE):

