8.2.3 Secondary Analyses

A per-protocol analysis will compare randomized groups among protocol adherent patients – here, defined among as those actually receiving the procedure and making $\geq 80\%$ follow-up visit in both groups. Modified ITT will be considered the primary approach for all efficacy analyses and will include patients who actually received the intervention regardless of adherence to follow-up visits. Safety endpoints and adverse events may be evaluated based on treated group (per-protocol).

Additional outcomes and analyses not specified here are considered exploratory and post-hoc and will be clearly identified as such in any publications.

^b %TBWL defined as $[(\text{pre-operative weight} - \text{post-operative weight}) / (\text{pre-operative weight})] \times 100$

^c % EWL defined as $[(\text{pre-op weight} - \text{follow up weight}) / (\text{pre-op weight} - \text{ideal body weight})] \times 100$

Note: "Ideal body weight" of BMI 25

Missing Data

The primary analysis uses a hierarchical regression model, assuming post-randomization dropout is missing at random (MAR) among subjects completing at least 1 of the planned follow up visits.

Patients excluded after randomization and before intervention on the basis of identified exclusion criteria will be excluded from analyses; reasons for meeting exclusion criteria will be documented. Patients that withdraw/dropout between randomization and intervention are assumed to be missing completely at random. However, a sensitivity analysis will compare withdrawn subjects to participating subjects and perform analyses under MAR (including multiple imputation) assumptions if these subjects appear different or if dropout occurs at substantially different rate in one arm compared to the other. Participating patients who dropout prior to the first follow up visit will be analyzed similarly.

Randomization and Data Collection

Stratified block randomization schedules will be uploaded to REDCap. Data will be collected in REDCap data collection forms.

Interim Analysis

No interim analysis will be performed for efficacy endpoints. Adverse events will be monitored throughout and discussed with the data monitoring committee.

ETHICAL CONSIDERATIONS

This study is to be conducted according to United States government regulations and Institutional research policies and procedures.

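### The stopping rule in section 7.11 joins its three criteria with "and", so as written an attributed death alone does not stop the study

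*Combined protocol and SAP*

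**What the plan says.** Section 7.11 is a single sentence, the core of which runs "one death attributed to the procedure or the device, b) >2 of Grade IV AEs has occurred, and c) > 4 Grade III". Its three lettered criteria are:

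- (a) "The study will be stopped if a) one death attributed to the procedure or the device"
- (b) "b) >2 of Grade IV AEs has occurred"
- (c) "and c) > 4 Grade III or more AEs occur"

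Nothing in the sentence says that one criterion is enough.

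The section just before it, Data and Safety Monitoring, describes how the rule is applied: "Ongoing assessment of AEs by the PI will determine if any of the stopping rules have been triggered".

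In section 7.2.1, Figure 2 (Clavien-Dindo grading) defines Grade V as "Death of a patient", so a death also counts towards criterion (c). Under Interim Analysis the plan adds: "Adverse events will be monitored throughout and discussed with the data monitoring committee". Neither that section nor Data and Safety Monitoring gives a criterion for halting.

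**The concern.** A list of conditions under one if, closed by and, is satisfied only when every condition is met. On that reading criterion (a) does nothing by itself: a death attributed to the procedure would have to be accompanied by at least three Grade IV events and at least five events of Grade III or higher in total. Criteria (b) and (c) would likewise have no force unless someone had died.

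That conflicts with the neighbouring section, which treats the rules as several and allows any of them to be triggered. The investigator, who is named as the person to apply the rule, has to override the wording of section 7.11 with a sentence from another section, possibly straight after a death. A safety rule should not need that step.

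**Working it through.** The plan states no operating characteristics for the rule, so there is no figure to reproduce. The check is a comparison of text and then a count.

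**Which reading does the document support?**

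| Place | What it shows |
|---|---|
| Section 7.11, sentence | One if, three criteria, joined by and |
| Section 7.11, heading | Rules, in the plural |
| Data and Safety Monitoring | Any of the rules may be triggered |
| Exclusion Criteria, item 27: "Subjects who are taking corticosteroids, immunosuppressants, and narcotics" | Separate conditions in a list closed with and |
| Section 7.2.1.2, SAE definition | States explicitly that meeting one criterion is enough |

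The second to fourth rows point to separate triggers as the intent. The last shows that the document can state alternatives plainly; section 7.11 does not.

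**How far apart are the two readings?** Inputs are the thresholds in section 7.11 and the grading in Figure 2. Let d be attributed deaths (Grade V), v Grade IV events and t Grade III events. Each event is counted once at its worst grade, and every death is taken as attributed. More than 2 means at least 3; more than 4 means at least 5.

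- Separate triggers: stop if d ≥ 1 **or** v ≥ 3 **or** d + v + t ≥ 5.
- Literal: stop if d ≥ 1 **and** v ≥ 3 **and** d + v + t ≥ 5.

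For n events in total, the number of mixes (d, v, t) is (n + 1)(n + 2)/2. With n ≤ 4, separate triggers fail to stop only when d = 0 and v ≤ 2. That leaves 2 mixes at n = 1 (v = 0 or 1) and 3 mixes at each of n = 2, 3 and 4 (v = 0, 1 or 2).

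| Events n | Mixes | Stop, separate triggers | Stop, literal |
|---|---|---|---|
| 1 | 3 | 3 − 2 = 1 | 0 |
| 2 | 6 | 6 − 3 = 3 | 0 |
| 3 | 10 | 10 − 3 = 7 | 0 |
| 4 | 15 | 15 − 3 = 12 | 0 |
| **1 to 4** | **34** | **23** | **0** |
| 5 | 21 | 21 | 3 |

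The literal column is zero up to n = 4 because the third condition needs five events. At n = 5 the mixes (d, v, t) that satisfy all three conditions are (1,3,1), (1,4,0) and (2,3,0). With d = 0 the literal rule is false for every v and t.

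The count needs no event rates. It treats all mixes alike and says nothing about how likely any of them is.

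**The case against.** The strongest reply is that the document already resolves the point. The adjacent section speaks of any of the rules, and the heading is plural. Item 27 of the exclusion criteria shows that the authors close lists of alternatives with and. Criteria (b) and (c) have their own verbs, so the and may do no more than end a lettered list. The thresholds themselves (1, more than 2, more than 4, at falling severity) make sense only as alternatives: under the literal reading one death and three Grade IV events already supply four of the five events that (c) requires. No investigator is likely to carry on after an attributed death on the strength of this conjunction.

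Oversight also does not rest on this sentence alone. There are monthly and as-needed meetings, IRB reporting, an IRB-approved data safety monitoring plan and a data monitoring committee, and nothing bars an earlier stop. The monitoring plan is not part of this document and may state the rules correctly. Finally, the count of mixes gives equal weight to very unequal combinations and uses a counting convention the protocol does not state.

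Most of this stands. The intent is clear enough, the practical risk is small, and the counts describe the gap between two readings, not expected harm. What does not follow is that the sentence is acceptable. Recoverable intent makes the correction uncontroversial, but the rule still has to be read against its own wording, and no other section here restates it.

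**Conclusion.** The concern holds as a drafting error in the only explicit halting rule in the document. As written, the study must stop only after at least five events, including an attributed death and three Grade IV events; as very likely intended, one attributed death is enough.

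That the sentence says and, with nothing to mark alternatives, rests on the text alone. The counts rest on each event being counted once at its worst grade and on all deaths being attributed. No claim is made about the probability of stopping, since the documents give no event rates by grade. The thresholds are not in question. The point should be corrected because it concerns patient safety, but it casts no doubt on the design or the analysis.

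**What to change.** Reword section 7.11 so that each criterion stands alone, for example:

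> Stop the study as soon as any one of the following has occurred: (a) one death attributed to procedure or device; (b) more than two Grade IV AEs; or (c) more than four AEs of Grade III or higher.

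The sponsor-investigator should also confirm that the data safety monitoring plan carries the same wording. The cost is a correction to one sentence, with no effect on thresholds, sample size or analysis.

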7.2.1 Definitions

The following definitions will be used:

7.2.1.1 Adverse Events:

Only untoward medical occurrence, unintended disease or injury, or untoward clinical signs (including abnormal laboratory findings) related to the study intervention. Each subject will be followed closely to ensure safety.

Adverse events will be classified using the Clavien-Dindo classification in Figure 2.

Figure 2. Adverse Event (AE) Clavien-Dindo Classification Grading

Grade	Definition
Grade I	Any deviation from the normal postoperative course without the need for pharmacological treatment or surgical, endoscopic, and radiological interventions Allowed therapeutic regimens are: drugs as antiemetics, antipyretics, analgetics, diuretics, electrolytes, and physiotherapy. This grade also includes wound infections opened at the bedside
Grade II	Requiring pharmacological treatment with drugs other than such allowed for grade I complications Blood transfusions and total parenteral nutrition are also included
Grade III	Requiring surgical, endoscopic, or radiological intervention
Grade IIIa	Intervention not under general anesthesia
Grade IIIb	Intervention under general anesthesia
Grade IV	Life-threatening complication (including CNS complications) requiring IC/ICU management
Grade IVa	Single organ dysfunction (including dialysis)
Grade IVb	Multiorgan dysfunction
Grade V	Death of a patient

7.2.1.2. Serious Adverse Event (SAE):

An adverse event that meets one of the following criteria

- Led to death
- Resulted in serious deterioration in the health of the subject that results in:
 - Life-threatening illness or injury
 - Permanent impairment of a body structure or a body function
 - The need for in-patient care or prolongation of hospitalization (this does not include the optional 23 hours observation admission after ESG or re-tightening procedure).
 - Medical or surgical intervention to prevent life-threatening illness or injury or permanent impairment to a body structure or a body function.
- **Planned hospitalization for a pre-existing condition, or a procedure required by the trial protocol, without serious deterioration in health, is not considered a serious adverse event**

Unanticipated problems, SAEs and AEs will be reported to governing IRBs per local guidelines.

For the purpose of the study, an adverse event is considered severe if it is grade ≥ 3 on the Clavien-Dindo classification.

7.2.1.3 Device-Related Adverse Event (DRAE):

An adverse event related to the use of the medical device. This definition includes any events resulting from incorrect delivery and operation of the device and/or of its approved accessories, or any malfunction of the device or its components. This definition also includes any event resulting from user error or from intentional misuse of the device.

7.2.1.4 Serious Device-Related Adverse Event (SDRAE):

Any untoward medical occurrence that can be attributed wholly or partly to the device, which resulted in any of the characteristics of a serious adverse event as described above.

7.2.1.5 Unanticipated Adverse Device Effects (UADE):

Any adverse device effect which by its nature, incidence, severity, or outcome, has not been identified under the SAE section 6.2.

Protocol Deviation

All protocol deviations will be documented with the subject number and date of the protocol deviation.

The following information will be documented for each protocol deviation:

- Inclusion/Exclusion exceptions or violations, including subject did not sign informed consent prior to study admission
- Follow-up visit not performed or Follow-up outside of window
- Required testing or questionnaire not performed
- Other (Describe)

Protocol deviations will be reported to the IRB at the time of continuing review unless they are determined to rise to the level of a major deviation and/or impact subject safety. In the event of a major deviation a report is to be made to the IRB within 5 working days. All deviations are to be recorded in the EDC.

Risk/Benefit evaluation

ESG is an established procedure that has an excellent safety profile and has been shown to demonstrate significant weight loss. APC is approved for use in the GI tract and has also been shown to have a good safety profile. Combining ESG with HAPC technique could enhance the durability of this procedure by enabling approximation of submucosal surfaces for enhanced gastroplasty healing. This could help maximize the metabolic benefits of gastric mucosal revitalization in conjunction with the restrictive effects of ESG for enhanced weight loss, durability, and metabolic benefits of the combined procedure while minimizing the risk of weight recurrence previously reported with the traditional ESG. Since both procedures have an established good safety profile, hence minimizing the risks about using them in conjunction.

STATISTICAL ANALYSIS

Power and Sample Size

The primary endpoint for power and sample size is durability of plications on repeat endoscopy 6 months after initial procedure with HAPC and ESG and ESG alone. Another primary endpoint for power and sample size is %TBWL at 6 and 12 months.

We plan a 1:1 randomization scheme that allocates to either HAPC ESG (12 patients) or ESG alone (12 patients). Given the pilot nature of this trial, no formal power calculation is feasible or warranted.

Statistical Analysis

Statistical analyses of randomized groups at 6 and 12 months will be performed based on a modified intent-to-treat (mITT) principle for efficacy analyses. Patients randomized but subsequently withdrawn or identified as meeting exclusion criteria prior to intervention (as applied to both the treatment and control arms) will be excluded from the analysis if the reason for exclusion is documented and unrelated to the randomized arm.

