ESG is a commonly performed procedure that has been shown to demonstrate significant weight loss. However, combining it with HAPC technique to enable approximation of submucosal surfaces for enhanced gastroplasty healing, durability of this procedure could be enhanced. This could help maximize the metabolic benefits of gastric mucosal revitalization in conjunction with the restrictive effects of ESG for enhanced weight loss, durability, and metabolic benefits of the combined procedure while minimizing the risk of weight recurrence previously reported with the traditional ESG.

STUDY OBJECTIVES

Assess the safety and durability of combined HAPC and ESG compared to traditional ESG

Assess weight loss and improvement in obesity related co-morbidities in combined HAPC and ESG compared to ESG alone.

STUDY DESIGN

General Description

This is a single-center, randomized, single-blinded clinical trial evaluating the efficacy and safety of combined HAPC and ESG for weight loss and improvement in obesity-related co-morbidities compared to ESG alone in participants with a BMI ≥ 30 and ≤ 40 kg/m² who have failed to achieve and maintain weight loss with a non-surgical management.

Participants will be recruited from outpatient clinical weight loss clinics and from study-related institutional review board (IRB) approved advertisements.

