- Improvement in obesity related comorbidities (blood pressure, fasting glucose, HbA1c, lipid panel, liver enzymes) at 6 and 12 months compared to baseline.
- Changes in gastric motility, volume, accommodation, and constructed gastroplasty on MRI at 6 months compared to baseline.
- Changes in gastric emptying evaluated by gastric emptying study at 6 months compared to baseline.
- Changes in liver biochemical panel, and glucose homeostasis parameters at 6 months compared to baseline between the two groups.

Safety

- The incidence, frequency, and severity of adverse events related to treatment with the device will be reported throughout the duration of the study.
- Goal is <5% rate of serious adverse events related to the device or procedure (as determined by the site PI). Serious adverse events will be classified in the Adverse Events table.

Study Setting

The study will be conducted at 1 US center, Mayo Clinic in Rochester, MN. The maximum enrollment will be limited to 24 participants. The expected enrollment period is 6 months.

Subjects

Participants will be adult patients (Ages 21 \geq and \leq 65) with a BMI \geq 30 and \leq 40 kg/m² that meet the eligibility criteria below. All eligibility criteria must be met at the time of randomization.

Inclusion Criteria

1. Age 21-65
2. BMI \geq 30 and \leq 40 kg/m²
3. Willingness to comply with the substantial lifelong dietary restrictions required by the procedure.
4. History of failure with non-surgical weight-loss methods.
5. Willingness to follow protocol requirements, including signed informed consent, routine follow-up schedule, completing laboratory tests, and completing diet counseling.

6. Residing within a reasonable distance from the investigator's office and able to travel to the investigator to complete all routine follow-up visits.
7. Ability to give informed consent.
8. Women of childbearing potential (i.e., not post-menopausal or surgically sterilized) must agree to use adequate birth control methods.

Exclusion Criteria

1. History of foregut or gastrointestinal (GI) surgery (except uncomplicated cholecystectomy or appendectomy).
2. Prior gastrointestinal surgery with sequelae, i.e. obstruction, and/or adhesive peritonitis or known abdominal adhesions.
3. Prior open or laparoscopic bariatric surgery.
4. Prior surgery of any kind on the esophagus, stomach, or any type of hiatal hernia surgery.

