^a Childbearing potential to be defined as women who are not yet post-menopausal who are not consistently utilizing an acceptable form of contraception. Acceptable forms of contraception to include hormonal methods such as oral contraceptives, patches, injections, vaginal ring, or implants, hormonal or copper intrauterine device, or history of surgical sterilization including tubal ligation or hysterectomy.

screening assessments will have the chance to review any questions with the study staff, as well as a recap of the follow-up schedule, and they will then receive their randomization assignment.

Recruitment efforts will be made by working with Mayo Clinic's Research Recruitment Services to develop marketing materials including a recruitment flyer in both print and digital formats, a social media recruitment plan leveraging Mayo Clinic's enterprise social media accounts for recruitment and other potential tactics to be determined after recruitment begins, directed towards the goal of boosting minority inclusion to be at least representative of the local population. Data will be pulled during the time of IRB submission and included to establish general targets justifying Exclusion #35 to help reserve spots for enrollment that are in-line with a representative population if they are not met by a certain threshold. At the time of this writing, Rochester, MN has demonstrated approximately 10% minority population.

Randomization

Participants will be randomly assigned to treatment or control group with a 1:1 allocation per a computer-generated randomization using variable block randomization.

Participants will be blinded to the results of randomization. They will remain blinded until the end of the study, or if there is medical or surgical safety concern. If any SAEs occur, subjects may be unblinded as defined by the Clavien-Dindo Grade III or above. Unblinding of subjects will be reported to IRB per local site IRB guidelines, if not meeting the criteria above. Measures will be taken to minimize or avoid bias in the study using "masking/blinding procedures." Randomization assignment will be recorded in the EDC and subject tracking, but will not be recorded within the EMR to reduce clinical team exposure to their randomized status for follow-up care. Research teams will not be blinded to the randomization results. Subjects will be asked to confirm with their study team if they have become aware of the procedure.

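### Section 7.2.1.1 admits only intervention-related events as adverse events, so AE and SAE counts by arm, and stopping counts (b) and (c), pass through an unblinded relatedness judgement

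*Combined protocol and SAP*

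**What the plan says.** Section 7.2.1.1 limits the basic term: "Only untoward medical occurrence, unintended disease or injury, or untoward clinical signs (including abnormal laboratory findings) related to the study intervention". Section 7.2.1.2 builds the SAE on it, as "An adverse event that meets one of the following criteria". Section 7.11 then counts AEs in two of its three stopping criteria: (b) more than two of Grade IV and (c) more than four of Grade III or above. Data and Safety Monitoring says who applies them: "Ongoing assessment of AEs by the PI will determine if any of the stopping rules have been triggered". The Randomization section states: "Research teams will not be blinded to the randomization results".

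Safety is a comparative aim. The first study objective reads "Assess the safety and durability of combined HAPC and ESG compared to traditional ESG". Section 8.2.3 allows safety to be analysed by treatment received. The statistical section names no test or estimator for adverse event rates.

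Three other places have relatedness wording of their own. The Safety endpoints say "The incidence, frequency, and severity of adverse events related to treatment with the device will be reported throughout the duration of the study", and they set the SAE target as "Goal is <5% rate of serious adverse events related to the device or procedure (as determined by the site PI". Criterion (a) in 7.11 requires a death to be attributed to the procedure or device.

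**The concern.** Relatedness is normally an attribute of a recorded event. Here it is a condition for the event to be an AE at all. A late hospitalisation or a bleed that staff consider unrelated falls outside the definition, so nothing in the plan requires it to be recorded as an AE in either arm.

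That matters for a new combination. The background cites one case report of ESG with APC and says no prospective controlled comparison has been done, so what should count as related is not yet well known. All-cause counts by arm would let a reader see an unexpected imbalance. Counts already filtered by people who know the arm may hide one or create one.

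**Working it through.** **No figure to reproduce.** The plan gives no expected event rate, alpha or power for safety. The point rests on definitions, so the first step is to trace which quantities depend on 7.2.1.1.

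| Quantity | Where | Source of the relatedness filter |
|---|---|---|
| General AE counts by arm | 7.2.1.1 | This definition |
| General SAE counts by arm | 7.2.1.2 | This definition, because an SAE is an AE |
| Stopping counts (b) and (c) | 7.11 | This definition, because they count AEs |
| Stopping criterion (a) | 7.11 | Its own attribution wording |
| <5% SAE goal | Safety endpoints | Its own wording |
| Device-related AE reporting | Safety endpoints | Its own wording |

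**Is there a repair elsewhere?** No section requires events to be collected whatever their cause, gives criteria for relatedness, or provides blinded or independent adjudication of events. The external blinded reader sees only the 6-month EGD video, for suture durability. Interim Analysis mentions a data monitoring committee once, gives it no role in attribution, and would have it discuss events already filtered.

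**Illustration of size.** Inputs from the plan: 24 patients, 12 per arm; (b) is reached at 3 or more Grade IV events, (c) at 5 or more of Grade III or above. Assumed here: a true event rate p, a share a of events judged related, at most one event per patient, and each criterion taken as a trigger by itself.

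*Comparison by arm.* With equal true rates, the recorded difference is p × (a₁ − a₂). For a₁ = 0.9 and a₂ = 0.6:
- p = 0.30: 0.30 × 0.30 = 9 points (expected counts 3.24 v 2.16 of 12)
- p = 0.50: 0.50 × 0.30 = 15 points (5.40 v 3.60)
- p = 0.80: 0.80 × 0.30 = 24 points (8.64 v 5.76)

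Swapping the shares reverses the sign. With a = 0.8 in both arms, the difference is zero but every count is 20% lower.

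*Stopping counts.* The chance of reaching r events is P(X ≥ r) with X ~ Binomial(24, p × a).
- Criterion (c), r = 5, p = 0.20: 54.0% at a = 1, 33.7% at a = 0.8 and 8.5% at a = 0.5 (p × a = 0.10). For p from 0.10 to 0.30, the range is 8.5-88.9% at a = 1 and 0.6-28.7% at a = 0.5.
- Criterion (b), r = 3, p = 0.10: 43.6% at a = 1 and 11.6% at a = 0.5. For p from 0.05 to 0.20, the range is 11.6-88.5% at a = 1 and 2.1-43.6% at a = 0.5.

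These values show sensitivity. They are not forecasts for this trial.

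**The case against.** The case for leaving the plan alone has real content.

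- **Traces remain.** Source Documentation requires medical-record source for serious adverse medical events, with no relatedness limit in that sentence. Vital signs, medications and the GERD questionnaire are collected at follow-up visits whatever the cause. Liver enzymes are secondary outcomes, and esophagitis is compared between arms under 8.2.2. A reader might infer that events judged unrelated are lost beyond review. The documents do not support that: some could be found again. These sources still do not amount to all-cause AE capture.
- **Oversight exists.** There is an IRB-approved monitoring plan, quarterly internal monitoring and a named committee. Assignment is kept out of the medical record to limit what the clinical team sees. None of this is given a role in judging relatedness, although the monitoring plan itself is not among the documents.
- **Who decides relatedness is only partly stated.** The PI is named for relatedness in the SAE goal and for AE assessment under the stopping rules. No one is named for ordinary AEs. It remains true that anyone on the research team who decides it would be unblinded.
- **The device-related categories still make sense.** A reader might infer that the definition empties the device-related categories. It does not: device-related events are a coherent subset of intervention-related events, and the serious device-related definition starts from any untoward occurrence attributable to the device.
- **It is a 24-patient pilot.** There is no formal power calculation, and both arms receive ESG, so related events can be counted in both. This limits the consequences but does not correct the counts.

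The word Only at the start of the definition may be a slip for Any. The relatedness clause restricts the term either way.

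**Conclusion.** The concern holds for the general AE and SAE counts by arm and for stopping counts (b) and (c). Followed as written, the plan passes these through an unblinded judgement before anything has to be recorded. The bias is a risk of unknown direction. Equal under-attribution lowers all counts, and unequal attribution distorts the comparison, by 9-24 points under the assumptions shown.

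A reader might infer that the <5% goal and all the stopping criteria inherit the problem, and measure it by one event in 24 (1/24 = 4.2%, goal met) against two (2/24 = 8.3%, goal missed). The documents do not support that. The goal and criterion (a) state their own relatedness condition, so that arithmetic would be the same after 7.2.1.1 is corrected. Nor do the documents say that the goal applies within each arm.

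This is a worthwhile and inexpensive improvement, best made before follow-up because events not captured then may be only partly recoverable. It does not invalidate the trial.

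**What to change.** 1. In 7.2.1.1, define an AE as any untoward medical occurrence from the procedure onward, whether or not considered related.
2. Add relatedness (procedure / device / neither) as a separate field on the Adverse Events Form.
3. Report all-cause AEs and SAEs by arm first, then the related subset. Keep the <5% goal on the related subset, shown beside the all-cause count. The related subset will still rest on unblinded judgement, but a reader will see what was left out of it.
4. The new definition would change what criteria (b) and (c) in 7.11 count. The sponsor must state whether they use all-cause or related events. It must also reconcile Data and Safety Monitoring, where the PI decides, with Interim Analysis, which brings in a data monitoring committee. Which basis to use is for the sponsor to decide.

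The cost is protocol wording and one field on a form the Schedule of Events already requires from the procedure onward. The downside is more minor events to enter and an all-cause rate that looks less favourable.
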